#### 8.1 Screening

At the screening visit, all study subjects must be thoroughly informed about all aspects of the study, including the study treatment, visit schedule, required evaluations, and all regulatory requirements for informed consent. For details of screening assessments, refer to Assessment schedule in Table 8-1. Assessments cannot be performed prior to signature of the informed consent. If the subject does not fulfill all inclusion/exclusion criteria, he/she must be documented as a screening failure (Section 8.1.1).

It is permissible to re-screen a subject if he/she fails the initial screening criteria. If the subject is re-screened, a new ICF must be obtained and re-screening will be documented in the subject's source documents. A new subject number will be allocated and the site will record data in a new CRF.

#### 8.1.1 Information to be collected on screening failures

[figure not shown]
All patients who have signed informed consent but not entered into the next epoch will have the study completion page for the screening Epoch, demographics, inclusion/exclusion, and serious adverse event (SAE) data collected. Adverse events that are not SAEs will be followed by the investigator and collected only in the source data.

### 8.2 **Subject demographics/other baseline characteristics**

Patient demographic and baseline characteristic data will be collected on all patients including: year of birth, age, sex, race, source of patient referral, relevant medical history/current medical condition present before signing informed consent for trial CAMG334ADE01 (HER-MES). Where possible, diagnoses not symptoms will be recorded.

Prior headache characteristics and previous headache medication history prior to treatment in trial CAMG334ADE01 (HER-MES), including information on the suitability for migraine prophylactics will be collected as part of baseline characteristics.

Investigators will have the discretion to record abnormal test findings on the medical history eCRF whenever in their judgment, the test abnormality occurred prior to the informed consent signature.

#### 8.4 **Safety/Tolerability**

Safety assessments will include:

- Treatment discontinuations due to AEs
- Adverse events (Section 10.1)
- Physical examination
- Vital signs
- ECG
- Height/weight
- Laboratory evaluations
- Pregnancy testing (females of childbearing potential)

Safety assessments are specified below with the assessment schedule detailing when each assessment is to be performed.

For details on AE collection and reporting, refer to AE section.

Table 8-2	Assessments & Specifications
Assessment	Specification
Physical examination	A complete physical examination will include the examination of general appearance, skin, neck (including thyroid), eyes, ears, nose, throat, lungs, heart, abdomen, back, lymph nodes, extremities, as well as vascular and neurological examination. If indicated based on medical history and/or symptoms, rectal, external genitalia, breast, and pelvic exams will be performed. A brief physical exam will include the examination of general appearance and will be at all visits starting from baseline visit, except where a complete
	physical examination is required (see above). Information for all physical examinations must be included in the source documentation at the study site. Clinically relevant findings that are present at screening must be included in the Medical History part of the eCRF. Significant findings made after first administration of investigational drug, which meet the definition of an Adverse Event must be recorded on the Adverse Event section of the eCRF.

Assessmen	Specification
Vital signs	Vital signs include blood pressure, pulse and temperature measurements. After the patient has been sitting for approximately five minutes, with back supported and both feet placed on the floor, systolic and diastolic blood pressure will be measured three times using a validated device, with an appropriately sized cuff. The repeat sitting measurements should be made at approximately 1 – 2 minute intervals and the mean of the three measurements will be used. In case increased blood pressure is recorded (systolic/diastolic) measurements have to be repeated at the end of the study visit for validation. In case the cuff sizes available are not large enough for the patient's arm circumference, a sphygmomanometer with an appropriately sized cuff may be used. The method to take temperature should be consistent throughout the study.
Height a weight	Height in centimeters (cm) and body weight (to the nearest 0.1 kilogram (kg) in indoor clothing, but without shoes) will be measured.

#### 8.4.1 Laboratory evaluations

#### Table 8-3 Laboratory Assessments

Test Category	Test Name
Hematology	Hematocrit, Hemoglobin, Platelets, Red blood cells, White blood cells, Differential (Basophils, Eosinophils, Lymphocytes, Monocytes, Neutrophils), Platelets
Chemistry	Albumin, Alkaline phosphatase, ALT , AST , Gamma-glutamyl-transferase (GGT), Lactate dehydrogenase (LDH), Calcium, Magnesium, Phosphorus, Sodium, Potassium, Creatinine, Creatine kinase, Direct Bilirubin, Indirect Bilirubin, Total Bilirubin, Blood Urea Nitrogen (BUN)
Coagulation	International normalized ratio [INR]), Activated partial thromboplastin time (APTT)
Pregnancy	Urine pregnancy test
Test	Serum pregnancy test

#### 8.4.2 Electrocardiogram (ECG)

Electrocardiograms (ECGs) must be recorded as outlined in the central ECG reading manual. The preferred sequence of cardiovascular data collection during study visits is ECG collection first, followed by vital signs, and blood. The Fridericia QT correction formula (QTcF) should be used for clinical decisions. Single 12 lead ECGs are collected. The original ECGs *printed on non-heat-sensitive paper*, appropriately signed, must be collected and archived at the study site. Each ECG tracing must be labeled with study number, patient initials, subject number, date and time, and filed in the study site source documents.

For any ECGs with subject safety concerns, two additional ECGs must be performed to confirm the safety finding and forwarded to the central ECG laboratory for assessment. A monitoring or review process should be in place for clinically significant ECG findings throughout the study and especially at baseline before administration of study treatment.

Novartis	Confidential	Page 38
Clinical trial protocol V01	Protocol No. CAMG334ADE03	•

[figure not shown]
Clinically significant abnormalities must be recorded on the CRF as either medical history/current medical conditions or adverse events as appropriate.

[figure not shown]
#### 8.4.3 **Pregnancy and assessments of fertility**

All pre-menopausal women who are not surgically sterile will have pregnancy testing. Serum pregnancy tests will be performed at the beginning and end of the study, with urine pregnancy tests performed at the remaining visits. Pregnancy tests during DBTE should be performed/registered by the investigator prior to dosing. The specific schedule is outlined in Table 8-1.

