Plasma levels of CGRP increase with advancement of pregnancy up to the time of delivery, followed by a sharp decline at term and postpartum in rats and humans. Endogenous CGRP may play an important role in maintaining normal fetoplacental development, fetal survival, and vascular adaptation during pregnancy. Women who are breastfeeding, pregnant, or planning to become pregnant are excluded from study participation, as well as patients who are unwilling to comply with the protocol-specified contraception requirements. All women of child-bearing potential will be screened for pregnancy at each study visit.

An external data monitoring committee was established to review the erenumab safety data for Phase 2b and Phase 3a studies, and based on these data, recommended continuation of the program. The need for a data monitoring committee (DMC) for this study was assessed, and deemed not necessary because erenumab was approved by FDA and EMA for migraine prophylaxis and the safety profile of erenumab was well characterized in 4 double-blind, placebo-controlled trials in over 2500 patients. The risk to patients in this trial will be minimized

Novartis	Confidential	Page 21
Clinical trial protocol V01	Protocol No. CAMG334ADE03	•

by compliance with the eligibility criteria, close clinical monitoring, and allowance of acute rescue medications.

Initial benefits for erenumab as a migraine prophylactic have been demonstrated in a Phase 2b trial (Amgen Study 20120178), in which 70 mg was established as the minimally effective dose in EM (Sun et al 2016) with a significant placebo-corrected reduction of 1.1 monthly migraine days compared to baseline, as well as positive results on most secondary endpoints, including 50% responder rate.

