#### 6.1.4 **Treatment duration**

The planned duration of treatment is 128 weeks for individual patients. However, each patient is eligible to one voluntary treatment interruption of up to 24 weeks (approximately 6 months) after an initial treatment duration of at least 12 weeks. After such a voluntary treatment interruption within the 128 weeks of the Treatment Epoch patients may return to the treatment schedule.

Subjects can be discontinued from treatment earlier due to unacceptable adverse events and/or at the discretion of the investigator or the subject.

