#### Confidential Protocol No. CAMG334ADE03

#### Table 8-1Assessment Schedule

	Screen															Follow up 
Visit number 	0	Baseline	V101	V102	V103	V104	V105	V106	V107	V108	V109	V110	V199	V201 – V20X	V101B	V301
End of week	-2 to 0	0	12	24	36	48	60	72	84	96	108	120	128	Every 12 weeks	NA	132
Obtain informed consent	х															
Demography	Х															
Medical history & prior medication 	х															
Complete Physical Exam	S												S		S	
Brief Physical Exam		S	S	S	S	S	S	S	S	S	S	S		S		S
Height	Х															
Weight	Х												Х		Х	
Vital Signs 	Х	Х	Х	Х	Х	Х	Х	Х	Х	Х	Х	Х	Х	Х	Х	Х
ECG	Х														Х	
Concomitant Medications		x	x	x	x	x	х	х	х	x	х	х	х	х	x	

Page 31

	Screen		During drug holiday	First visit after drug holiday	Follow up 											
Visit number 	0	Baseline	V101	V102	V103	V104	V105	V106	V107	V108	V109	V110	V199	V201 – V20X	V101B	V301
End of week	-2 to 0	0	12	24	36	48	60	72	84	96	108	120	128	Every 12 weeks	NA	132
Adverse Events 	Х	х	х	х	х	х	х	х	Х	х	х	х	Х	Х	х	х
Serious Adverse Events⁵	х	x	x	х	х	х	х	х	х	х	х	х	Х	х	x	х
Study Drug dispensing 		х	х	х	Х	Х	Х	х	х	x	х	х			x	
Chemistry/Hematology 8	Х														x	x
Urine pregnancy 		х	x	x	х	х	х	х	х	х	х	х	Х			
Serum Pregnancy	х														x	x
		· 						· 			 	 				

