#### Confidential Protocol No. CAMG334ADE03

Novartis

Clinical trial protocol V01

Page 32

Novartis	Confidential	
Clinical trial protocol V01	Protocol No. CAMG334ADE03	

	Screen					Ope	n-label	Treatm	ent Epo	och				During drug holiday	First visit after drug holiday	Follow up 
Visit number 	0	Baseline	V101	V102	V103	V104	V105	V106	V107	V108	V109	V110	V199	V201 – V20X	V101B	V301
End of week	-2 to 0	0	12	24	36	48	60	72	84	96	108	120	128	Every 12 weeks	NA	132
Open-label Treatment Phase Completion form													х			
Follow-Up Phase Completion form																x

1 – All study visit target dates are to be calculated from the Day 1 visit date and all study procedures for a given visit should be completed on the same day.

2 – The Follow-Up Visit is required 8 weeks after last IMP injection (erenumab). The Follow-Up visit can be skipped if any other safety follow up visit occurred 4 weeks after last study visit. 3 – Including prior prophylactic medication.

4 – Includes blood pressure, pulse and temperature.

5 – SAEs will be collected after signing of the informed consent through the end of the Follow-Up Epoch end of study. Non-serious AEs will be collected starting at Baseline Visit through the end of the Follow-Up Epoch.

6 – Study drug erenumab will be dispensed to the patient at the center during the applicable study visit for home application. Last study drug application will be at week 124.

8 - Should be additionally performed at any visit if deemed necessary by the investigator due to AEs

9 Should be performed/registered by the investigator prior to dosing during DBTE.

X = Assessment to be recorded in the source documents and the clinical data base; S = Assessment to be recorded as source documentation only.

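### Table 8-1 schedules no pregnancy test at the drug-holiday visits V201–V20X, although Protocol sections 4.3 and 8.4.3 promise one

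*Protocol*

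**What the plan says.** Two places in the Protocol promise testing throughout. In section 4.3, as part of the risk-benefit argument: "All women of child-bearing potential will be screened for pregnancy at each study visit". In section 8.4.3: "Serum pregnancy tests will be performed at the beginning and end of the study, with urine pregnancy tests performed at the remaining visits". The same section then says "Pregnancy tests during DBTE should be performed/registered by the investigator prior to dosing" and refers to Table 8-1 for the schedule.

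Table 8-1 has two pregnancy rows. The urine row is marked from Baseline to V199. The serum row is marked at Screen, at V101B (the column headed "First visit after drug holiday") and at V301. Footnote 9, attached to the urine row only, reads "Should be performed/registered by the investigator prior to dosing during DBTE". On supply, footnote 6 says "Study drug erenumab will be dispensed to the patient at the center during the applicable study visit for home application".

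Sections 3 and 6.1.4 allow one voluntary interruption of up to 24 weeks, after at least 12 weeks of treatment. Table 8-1 places visits every 12 weeks during it. On the return, section 6.1.4 says: "After such a voluntary treatment interruption within the 128 weeks of the Treatment Epoch patients may return to the treatment schedule".

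**The concern.** A promise of testing at every visit and a schedule that leaves out one kind of visit cannot both be followed. Sites work from the schedule, so the test at the holiday visits will in practice not be done.

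Section 4.3 itself explains that endogenous CGRP may matter for fetal development and offers pregnancy screening as one of the protections. Pregnancy is a mandatory reason to stop treatment (section 9.1.1) and must be reported within 24 hours of becoming known (section 10.1.4). Both safeguards act only once the pregnancy is known.

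Nor is a holiday visit always remote from exposure. Exclusion criterion 13 sets contraception for 110 days after stopping medication. The first holiday visit comes 84 days after the visit at which the holiday began. If the last injection was no more than 110 − 84 = 26 days before that starting visit, the 110 days have not yet run out.

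A smaller concern is the pre-dose rule. It is tied to an epoch name that this trial does not use, and it does not say that the result must be known and negative before erenumab is resumed.

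**Working it through.** The plan states no figure on this point, so there is nothing to reproduce. The check is a reading of Table 8-1 followed by day arithmetic.

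**Step 1: the table by column.** The table has 16 visit columns. The vital-signs row is marked in all 16, and the chemistry/hematology row shows the same pattern as the serum row, so the alignment is sound.

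| Visit | Urine test | Serum test | Erenumab dispensed |
|---|---|---|---|
| Screen | no | yes | no |
| Baseline, V101–V110 | yes | no | yes |
| V199 | yes | no | no |
| V201–V20X | **no** | **no** | no |
| V101B | no | yes | yes |
| V301 | no | yes | no |

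V201–V20X is the only visit type with no pregnancy test at all. It is also a visit type at which no drug is handed out.

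**Step 2: interval between scheduled tests.** Inputs: on-treatment visits every 12 weeks, with intervals of at most 84 ± 7 days (section 8); holiday of at most 24 weeks (sections 3 and 6.1.4); holiday visits every 12 weeks (Table 8-1). Assume that a holiday of *w* weeks starts at a scheduled visit where the urine test is done, and that V101B falls on the day the holiday ends. The interval is then 7 × *w* days.

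- On treatment: 7 × 12 = 84 days (84 + 7 = 91 at the edge of the window).
- Holiday of 12 weeks: 7 × 12 = 84 days, and 84 / 84 = 1.0, so no excess.
- Holiday of 24 weeks: 7 × 24 = 168 days, and 168 / 84 = 2.0.
- Holiday of 24 weeks with a urine test at the week-12 holiday visit: 84 days, then 168 − 84 = 84 days.

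For holidays between 12 and 24 weeks the excess is 7*w* − 84 days, at most 84. One untested holiday visit accounts for all of it.

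**Step 3: the pre-dose rule.** DBTE appears in neither the abbreviation list nor the glossary. Section 3 names three epochs: Screening, Open-label Treatment and Follow-up. Dosing occurs only in the second, so that is the natural meaning. Section 6.1.4 places the return from a holiday within the Treatment Epoch, so the sentence in 8.4.3 covers the V101B serum test. Footnote 9 does not reach it, because it belongs to the urine row, which is blank at V101B. In both places the rule asks that the test be performed or registered before dosing; neither mentions the result.

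**The case against.** The best defence is that testing is placed where exposure resumes. No drug is given at V201–V20X. V101B works as a second baseline, with a complete physical examination, ECG, chemistry/hematology and serum pregnancy test. Section 8.4.3 names Table 8-1 as the specific schedule, so sites have one controlling source. Section 14 allows extra safety assessments case by case, and any pregnancy that becomes known must be reported. The factor of 2.0 compares an off-drug interval with on-drug intervals and needs the longest permitted holiday.

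Much of this stands: it limits the consequence to later detection. It does not resolve the contradiction. That the table controls is exactly why the promise in section 4.3 goes unmet, and a discretionary test is not a scheduled one.

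A reader might infer four stronger things that the documents do not support:

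- *That the protocol permits dosing in pregnancy at V101B.* A serum test is scheduled there, the 8.4.3 rule covers it on the natural reading, registering a test can fairly mean recording its result, and pregnancy bars entry and requires discontinuation.
- *That drug will be handed out before the serum result is back.* The documents do not say where that test is read or how quickly. Section 10.2.1 names a central laboratory for repeat liver chemistry, which is a different test. The rule also governs dosing, which takes place at home, so dispensing at the visit does not itself breach it.
- *That the test-free interval is 28 days longer.* SAP section 2.1.1.1 starts the actual holiday 28 days after the planned last dose, but that definition serves the analysis and is not a visit rule. The Protocol caps the interruption itself at 24 weeks.
- *That contraception lapses during a long holiday.* The 110 days run from stopping medication. Section 9.1.1 distinguishes a planned holiday from discontinuation, and section 7 ties contraception to taking part in the study.

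**Conclusion.** The point holds as an inconsistency with a modest safety consequence. In the longest permitted holiday, one scheduled visit passes without the promised test and the gap between scheduled tests doubles. The doubling rests on the two timing assumptions in Step 2; Table 8-1 gives no fixed week for V101B. The documents do not give the number of women of child-bearing potential or of holiday takers, so the number affected cannot be estimated. No estimate or analysis is touched.

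The wording around V101B is a secondary clarification: a safeguard that is implied should be stated outright.

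**What to change.** Main change: mark a urine pregnancy test at V201–V20X in Table 8-1, so that it agrees with sections 4.3 and 8.4.3.

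Clarification: in section 8.4.3 and footnote 9, replace DBTE with Open-label Treatment Epoch. Attach footnote 9 to the V101B serum test as well. State that its result must be negative before the first dose after the holiday.

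The cost is an amendment to one table row and two sentences, plus one inexpensive urine test per holiday visit. Those visits already take place, with vital signs recorded. The negative-result condition could delay a first home injection until the serum result is available; how long that takes is not stated.

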#### 8.4.4 Appropriateness of safety measurements

The safety assessments have been selected based upon the safety profile of the drug as reported in the Investigator Brochure and are standard for this patient population and drug class.

# 9 Study discontinuation and completion

# 9.1 **Discontinuation**

## 9.1.1 **Discontinuation of study treatment**

Discontinuation of study treatment for a subject occurs when study treatment is stopped earlier than defined in the protocol and not for a planned "drug-holiday", and can be initiated by either the subject or the investigator.

The investigator must discontinue study treatment for a given subject if, he/she believes that continuation would negatively impact the subject's well-being.

Study treatment must be discontinued under the following circumstances:

- Subject/guardian decision
- Pregnancy
- Use of prohibited treatment as per recommendations in the prohibited treatment section
- Any situation in which study participation might result in a safety risk to the subject
- Any laboratory abnormalities that in the judgment of the investigator, taking into consideration the patient's overall status, prevents the patient from continuing participation in the study

If discontinuation of study treatment occurs, the investigator should make a reasonable effort to understand the primary reason for the subject's premature discontinuation of study treatment and record this information.

Subjects who discontinue study treatment or who decide they do not wish to participate in the study further should NOT be considered withdrawn from the study UNLESS they withdraw their consent (see withdraw of informed consent section,). Where possible, they should return for the assessments indicated in the assessment schedule. If they fail to return for these assessments for unknown reasons, every effort (e.g. telephone, e-mail, letter) should be made to contact the subject/pre-designated contact as specified in the lost to follow-up section. This contact should preferably be done according to the study visit schedule.

If the subject cannot or is unwilling to attend any visit(s), the site staff should maintain regular telephone contact with the subject, or with a person pre-designated by the subject. This telephone contact should preferably be done according to the study visit schedule.

After study treatment discontinuation, at a minimum, in abbreviated visits, the following data should be collected at clinic visits or via telephone/email contact:

- New / concomitant treatments
- Adverse Events/Serious Adverse Events

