### 3 Study design

This is an open-label, multi center, single arm study with flexible dosing allowing both dose adjustment and one drug holiday per patient.

The study design consists of 3 parts:

- Screening Epoch (0 2 weeks): required for all patients to assess initial eligibility.
- **Open-label Treatment Epoch (128 weeks):** Individual patients are treated for 128 weeks in the open-label treatment phase. During this open-label Treatment Epoch the erenumab dose may be adjusted from 70 mg to 140 mg or vice versa by discretion of the physician at any scheduled study visit. Additionally, a voluntary single treatment interruption ('drug holiday') of up to 24 weeks (approximately six months) may be introduced after at least 12 weeks of treatment in the open-label Treatment Epoch.
- Follow-up Epoch (4 weeks): A Follow-Up Visit 4 weeks after the last regular study visit (8 weeks after last IMP application) will be required as part of routine safety monitoring.

End of trial will occur when the last patient completes last visit (LPLV).

Figure 3-1	Study Design	
Screening Epoch Week -2 to Day -1	Open-label Treatment Epoch Day 1 to Week 128	Safety Follow-Up Epoch Week 128 to Week 132
	70 mg or 140 mg erenumab	
	optional drug	*

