## 10.1.3 **SAE reporting**

To ensure subject safety, every SAE, regardless of causality, occurring after the subject has provided informed consent and until completion of the Follow-Up Epoch (8 weeks after last IMP injection). must be reported to Novartis safety within 24 hours of learning of its occurrence. Detailed instructions regarding the submission process and requirements are to be found in the investigator folder provided to each site.

Migraine days including migraine-related events (underlying disease) which meet SAEdefinition (e.g. hospitalization) should be reported on the relevant eCRF pages instead of SAE form unless, in the judgement of the investigator, a migraine attack is unusually severe or unexpected and warrants specific notification as an SAE.

All follow-up information for the SAE including information on complications, progression of the initial SAE and recurrent episodes must be reported as follow-up to the original episode within 24 hours of the investigator receiving the follow-up information.

Novartis	Confidential	Page 45
Clinical trial protocol V01	Protocol No. CAMG334ADE03	-

An SAE occurring at a different time interval or otherwise considered completely unrelated to a previously reported one must be reported separately as a new event.

If the SAE is not previously documented in the Investigator's Brochure or Package Insert (new occurrence) and is thought to be related to the study treatment, a CMO & PS Department associate may urgently require further information from the investigator for health authority reporting. Novartis may need to issue an Investigator Notification (IN) to inform all investigators involved in any study with the same study treatment that this SAE has been reported.

Suspected Unexpected Serious Adverse Reactions (SUSARs) will be collected and reported to the competent authorities and relevant ethics committees in accordance with EU Guidance 2011/C 172/01 or as per national regulatory requirements in participating countries.

Any SAEs experienced after completion of the Follow-Up Epoch (8 weeks after last IMP injection) should only be reported to Novartis Safety if the investigator suspects a causal relationship to study treatment.

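### For patients whose last dose is before week 124 and who keep consent, the protocol gives two end points for AE collection and does not say which governs

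*Protocol*

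**What the plan says.** **Longer end point.** Protocol 9.1.1 states that stopping study treatment is not withdrawal from the study unless consent is withdrawn. Of such patients it says: "Where possible, they should return for the assessments indicated in the assessment schedule". If they do not attend, the site keeps in telephone contact, preferably on the visit schedule. AEs and SAEs are among the minimum data, and no earlier stop is given. Two other places fit this reading:
- Figure 3-1: "Safety Follow-Up Epoch Week 128 to Week 132".
- Table 8-1 footnote 1: "All study visit target dates are to be calculated from the Day 1 visit date".

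**Shorter end point.** Three statements point to 8 weeks after the last injection:
- Table 8-1 footnote 2: "The Follow-Up Visit is required 8 weeks after last IMP injection (erenumab").
- Table 8-1 footnote 5: "Non-serious AEs will be collected starting at Baseline Visit through the end of the Follow-Up Epoch".
- Protocol 10.1.3, on how long every SAE must be reported: "until completion of the Follow-Up Epoch (8 weeks after last IMP injection"). After that point only SAEs with a suspected causal link go to the sponsor's safety department.

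**Unclear for SAEs.** Footnote 5 names two end points in one phrase: "SAEs will be collected after signing of the informed consent through the end of the Follow-Up Epoch end of study".

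**Minimum only.** Protocol 10.1.1 requires AE monitoring for no less than eight weeks after the last dose. It sets a floor, not an end.

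**Analysis window.** AE tables count events that start in the on-treatment period. That period runs to 84 days after the last dose in SAP 2.1.1.1 and to 112 days in Protocol 12.5.2.

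**The concern.** Both rules describe the same visit for a patient dosed as planned. They separate for anyone whose last dose comes earlier, and two sites could follow the protocol in good faith and collect different data. A site that takes the Follow-Up Epoch as 8 weeks after the last injection would close non-serious AE collection at day 56. A site that follows 9.1.1 would go on to week 132.

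Long-term safety is the primary objective, and patients who stop because of an adverse event are among those affected. An event that no one asked about usually cannot be recovered at analysis. A thin late part of the on-treatment period could then be read as an absence of events when it partly reflects an absence of questions.

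**Working it through.** **Inputs**
- Planned last dose: Table 8-1 footnote 6, "Last study drug application will be at week 124".
- Follow-Up Visit V301: week 132 (Table 8-1).
- Shorter rule: 8 weeks, or 56 days, after the last injection (footnote 2, 10.1.3).
- On-treatment window: 84 days (SAP 2.1.1.1).
- Injection interval: 28 days (Protocol 4.2).

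**Step 1: the plan's own figure.** Protocol section 3 equates 4 weeks after the last regular visit with 8 weeks after the last dose. For the planned course, 128 + 4 = 132 and 124 + 8 = 132, so (132 − 124) × 7 = 56 days. This reproduces.

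**Step 2: last dose at week T before 124.** The shorter rule ends at week T + 8 and the longer at week 132. The difference is 132 − (T + 8) = 124 − T weeks. The disputed days inside the SAP window are min(84 − 56, 7 × (124 − T)).

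| Last dose (week T) | Shorter end (week) | Longer end (week) | Difference (weeks) | Disputed days in the 84-day window |
|---|---|---|---|---|
| 12 | 20 | 132 | 112 | 28 |
| 24 | 32 | 132 | 100 | 28 |
| 48 | 56 | 132 | 76 | 28 |
| 72 | 80 | 132 | 52 | 28 |
| 96 | 104 | 132 | 28 | 28 |
| 120 | 128 | 132 | 4 | 28 |
| 124 | 132 | 132 | 0 | 0 |

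With injections every 28 days, any on-schedule last dose before week 124 leaves the full 28 days in dispute: 28/84 = 33% of the post-dose window.

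**Step 3: does 9.1.1 already cover those days?** Yes. For T = 24, the next scheduled contact after week 32 is week 36, which is (36 − 24) × 7 = day 84. For T = 120, V301 is (132 − 120) × 7 = day 84.

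**Step 4: which outputs depend on it?**
- *TEAE tables*: events starting in days 57–84. Later AEs fall outside the SAP window under either rule.
- *AE and SAE listings and the post-treatment death summary*: these have no 84-day limit, so the whole 124 − T weeks could matter. For unrelated SAEs and deaths this is only possible. 10.1.3 governs reports to the safety department, and collection under 9.1.1 may continue.
- *Primary rate*: time under treatment ends 28 days after the last dose (SAP 2.1.1.1). The other patient-years definition in that section does not use the 84-day window either. Events from days 57–84 could enter the numerator only if AEs were counted over the whole on-treatment period.
- *Discontinuation proportions*: unaffected, because the reason is recorded when treatment stops.

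**The case against.** The best defence is that the documents allow a coherent week-132 reading. 9.1.1 is the specific rule for early stoppers. Figure 3-1 fixes the Follow-Up Epoch by calendar, and footnote 1 counts visit dates from Day 1. The main clause of section 3 and the second sentence of footnote 2 both count 4 weeks from the last study visit, which is week 132 for a patient kept on schedule. Protocol 9.1.3 does not treat a patient as lost until due diligence is complete or the study ends. AEs volunteered between visits are also recorded (10.1.1).

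All of this stands, and it limits the point to what a site may do. It does not remove the point, because footnote 2 and 10.1.3 state the other anchor in plain terms and the floor in 10.1.1 is met by either practice.

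A reader might infer three stronger things that the documents do not support:
- **That late events are lost.** No document shows that any site would stop at 8 weeks, and for unrelated SAEs and deaths even the rule is unclear.
- **That the disputed days measure bias.** They could be converted to 100 × 28/365.25 = 7.7 person-years per 100 early stoppers. But TEAE tables report numbers and percentages of subjects, and no planned denominator uses the 84- or 112-day window.
- **That completers need an extra call or a shorter window.** After a week-124 dose, V301 is day 56 and the SAP window runs to week 136 (124 + 12), so 28 days have no scheduled contact. A window longer than collection is an inclusion rule for events that happen to be reported, and shortening it would discard them. The gap is not universal either: a patient whose drug holiday runs to the end, with a last dose at week 120, has V301 on day 84.

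**Conclusion.** The point holds as an unresolved inconsistency and is a modest, optional improvement. For a patient with an on-schedule last dose before week 124 who keeps consent, the two rules differ by 124 − T weeks, and 28 of the SAP's 84 post-dose days are in dispute. The loss arises only at a site that takes the shorter reading. It concerns non-serious AEs in days 57–84 and, less certainly, later unrelated SAEs and deaths.

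The effect is confined to descriptive TEAE tables, listings and the post-treatment death summary. The primary rate is little affected.

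This assumes that visits fall on their target dates. It also assumes that the SAP's 84 days define the tables; under the protocol's 112 days the disputed part would be 56 days for a last dose by week 116. That difference between the two documents is a separate matter. The documents give neither the proportion of patients who stop drug but keep consent nor an AE rate for the late days, so no count of missed events, bias or study total follows.

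**What to change.** In Table 8-1 footnotes 2 and 5 and in Protocol 10.1.3, give one end point. Suggested wording: *For every patient who has not withdrawn consent, including a patient on a drug holiday at study end, AEs, SAEs and deaths are collected until the later of week 132 and 8 weeks after the last dose, by telephone where the patient does not attend.*

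Drug holidays need naming because 9.1.1 excludes a planned holiday from its definition of discontinuation. Without this, such a patient would be neither an early stopper nor dosed at week 124. For any last dose up to week 124 the rule gives week 132. The 8-week limb matters only if a last dose slips later.

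The cost is a wording change, plus schedule calls for early stoppers at sites that would otherwise stop at 8 weeks. A patient last dosed at week 24 has ten contacts left after week 32 (weeks 36, 48, 60, 72, 84, 96, 108, 120, 128 and 132). One last dosed at week 96 has four after week 104 (weeks 108, 120, 128 and 132). 9.1.1 already asks for these contacts.

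For completers dosed to week 124, state in the study report that days 57–84 after the last dose had no scheduled contact. No extra call or shorter window is required.
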